#### What we will do with the sample:

Briefly, samples will be collected at home by the study participants into Zymo fecal collection tubes which contain a reagent to stabilise DNA at ambient temperature. Samples were returned by mail within 2 weeks and stored at -80°C until processed. DNA will be extracted from pelleted samples using the appropriate DNA Isolation kit. We will perform 16S rRNA sequencing and/or metagenomic sequencing to profile the composition of the microbiota in the sample and the metagenome encoded by the microbiota. qPCR will be utilised to quantify bacterial load and quantify specific bacterial populations. We will then determine whether the composition or metagenome-encoded function of the stool microbiota is correlated with either specific or non-specific immune responses to the BCG vaccine. We will also assess whether the composition of the stool microbiota is associated with any of the other primary, secondary, or exploratory outcomes described in the study protocol. Furthermore, we will characterise the composition of the stool microbiota in participants in the trial and investigate whether the composition of the microbiota is altered at 3 or 12 months later. We will assess whether immunisation with BCG leads to an altered microbiota at 3 or 12 months compared to participants receiving the placebo.

## 17.3 Appendix 3 UK Specific Requirements

In the UK, the Competent Authority (MHRA) required the following two UK specific requirements:

- 1. In the UK, a negative pregnancy test is required for all WOCBP to confirm eligibility for the trial.
- 2. In the UK, the responsibility to break the treatment code in emergency situations resides solely with the UK Principle Investigator and will not be delayed by requiring other study staff in Australia such as the Chief Investigator or medical monitor to be involved in the decision to un-blind. The study code will only be broken for valid medical or safety reasons e.g. in the case of a severe adverse event where it is necessary for a treating physician (Requester) to know which intervention the participant has received, in order to manage the participant's condition appropriately.

The Requester contacts the local Principal investigator (PI), or delegate, to discuss the pros and cons of breaking the code. If the consensus is to break the code, the Requester contacts the holder of the code break list. In the UK, this has been delegated to the UK based Data Manager who will provide the Requester with the information on allocated group on direction from the PI. On receipt of the allocation details the Requester deals with the participant's medical emergency as appropriate. Should this code-breaking protocol be activated, the Chief Investigator will be alerted at the earliest opportunity, and within 2 working days at the latest.

#### Woman of Child Bearing Potential:

For the purpose of this document, a woman is considered of childbearing potential (WOCBP), i.e. fertile, following menarche and until becoming post-menopausal unless permanently sterile. Permanent sterilisation methods include hysterectomy, bilateral salpingectomy and bilateral oophorectomy. A postmenopausal state is defined as no menses for 12 months without an alternative medical cause. A high follicle stimulating hormone (FSH) level in the postmenopausal range may be used to confirm a post-menopausal state in women not using hormonal contraception or hormonal replacement therapy. However in the absence of 12 months of amenorrhea, a single FSH measurement is insufficient.

## 17.4 Appendix 4 Brazil Specific Requirements

#### SARS-CoV-2 Screening test

Due to public interest in determining the extent of asymptomatic SARS-CoV-2 infection in healthcare workers in Brazil, the Brazilian investigators will use the BRACE participants to estimate this prevalence rate. Therefore after enrolment a baseline respiratory swab will be collected by the study nurse. The swab samples will be analysed by PCR for detection of SARS-CoV-2 and participants advised when results are confirmed. Participants who return a positive SARS-CoV-2 result on the baseline swab will remain in the trial. In Mato Grosso do Sul, the samples will be analysed in batch months after randomisation, so there will be no clinically actionable results. Results will be shared with participants approximately 3 months after randomisation, for participant who return a positive SARS-CoV-2 result, the site will be required to report the participant's positive SARS-CoV-2 results to the applicable health agencies. They will be told that they will not be informed of their result before then. In Rio de Janeiro, due to high transmission rates, samples will be tested immediately and reported to participants. PCR tests will be conducted by the study lab team and the results reported to health agencies by a system called e-SUS VS, which constitutes a database of several diseases, including COVID-19, which is mandatory.

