## Оитсомея Primary outcomes: 1. Symptomatic COVID-19 defined as: AND OUTCOME **MEASURES** a positive SARS-CoV-2 test (PCR, RAT or serology) over the 6 months following randomisation PLUS • fever (using self-reported questionnaire)OR • at least one sign or symptom of respiratory disease, including cough, sore throat, shortness of breath, respiratory distress/failure (using self-reported questionnaire) 2. Severe COVID-19 defined as: a positive SARS-CoV-2 test (PCR, RAT or serology) over the 6 months following randomisation PLUS • Death (as a consequence of COVID-19) • Hospitalised (including mechanical ventilation and death), OR Non-hospitalised severe disease, defined as Non-ambulant for $\geq$ 3 consecutive days OR Unable to work for $\geq$ 3 consecutive  "pretty much confined to bed (meaning finding it very difficult to do any normal daily activities"  "I do not feel physically well enough to go to work" Secondary outcomes: All assessed at 6 and 12 months following randomisation unless otherwise indicated. The following outcomes are for both COVID-19 and fever or respiratory illness: presence of disease, days unable to work, days confined to bed, of days with symptoms, pneumonia, need for oxygen therapy, admission to critical care, need for mechanical ventilation Symptomatic or severe COVID-19, fever or respiratory illness Time to first symptom of COVID-19, fever or respiratory illness Deaths Number of days of unplanned absenteeism Type and severity of local and systemic adverse event over the 3 months following randomisation Planned exploratory analyses: episodes of and time to first recurrence of herpes simplex recurrence, immunological studies 7244 adult healthcare workers from Brazil, Europe and Australia TRIAL **POPULATION** (Victoria, Western Australia, South Australia and New South Wales) will be involved in the study, plus 2834 recruited in the earlier stage of this study. Key exclusion criteria are having BCG vaccine

contraindication, previously had a SARS-CoV-2 positive test result and prior involvement in this trial at an alternate study site. Participants will be randomised at 1:1 ratio giving approximately 5039 per group.

Multiple sites will enrol healthcare workers in Brazil, Europe and

Study Name: BCG vaccination to Reduce the impact of COVID-19 in healthcare workers (BRACE) trial RCH HREC number: 62586

Australia.

Version & date: version 12.0 dated 17May2022

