## 4.3.3 Exclusion criteria

- Has any BCG vaccine contraindication
  - o Fever or generalised skin infection (where feasible, randomisation can be delayed until cleared)
  - Weakened resistance toward infections due to a disease in/of the immune system
  - Receiving medical treatment that affects the immune response or other immunosuppressive therapy in the last year.
    - These therapies include systemic corticosteroids (≥20 mg for ≥2 weeks), non-biological immunosuppressant (also known as 'DMARDS'), biological agents (such as monoclonal antibodies against tumour necrosis factor (TNF)-alpha).
    - People with congenital cellular immunodeficiencies, including specific deficiencies of the interferon-gamma pathway
    - People with malignancies involving bone marrow or lymphoid systems
  - o People with any serious underlying illness (such as malignancy)
    - NB: People with cardiovascular disease, hypertension, diabetes, and/or chronic respiratory disease are eligible if not immunocompromised, and if they meet other eligibility criteria

- o Known or suspected HIV infection,  even if they are asymptomatic or have normal immune function.
  - This is because of the risk of disseminated BCG infection 12,13
- o People with active skin disease such as eczema, dermatitis or psoriasis at or near the site of vaccination
  - A different adjacent site on the upper arm can be chosen if necessary

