## o Pregnant

- Although there is no evidence that BCG vaccination is harmful during pregnancy, it is a contraindication to BCG vaccination. Therefore, we will exclude women who think they could be pregnant or are planning to become pregnant within the next month.
- UK specific: Although there is no evidence that BCG vaccination is harmful during pregnancy, it is a contraindication to BCG vaccination. Therefore, we will exclude women of childbearing potential (WOCBP) who think they could be pregnant. See section 8.2 for definition of WOCBP and Appendix 3 for UK specific pregnancy test requirements.
- Spain specific: If the patient is female, and of childbearing potential, she must have a negative pregnancy test (provided by Sponsor) at the time of inclusion and practice a reliable method of birth control for 30 days after receiving the BCG vaccination. See Appendix 6 for Spain specific requirements
- o Another live vaccine administered in the month prior to randomisation
- Require another live vaccine to be administered within the month following BCG randomisation
  - If the other live vaccine can be given on the same day, this exclusion criteria does not apply
- Known anaphylactic reaction to any of the ingredients present in the BCG vaccine
- o Previous active TB disease
- Currently receiving long term (more than 1 month) treatment with isoniazid, rifampicin or quinolone as these antibiotics have activity against Mycobacterium bovis
- Previous adverse reaction to BCG vaccine (significant local reaction (abscess) or suppurative lymphadenitis)
- BCG vaccine given within the last year

- Have previously had a SARS-CoV-2 positive test result (positive PCR on a respiratory sample or a positive SARS-CoV-2 diagnostic RAT test approved by the local jurisdiction's public health policy)
- Already part of this trial, recruited at a different site/hospital.
- Participation in another COVID-19 prevention trial
- Have previously received a COVID-19-specific vaccine

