#### **Blood samples**

- At randomisation, a blood sample will be taken for later assessment of seroconversion (production of specific anti-SARS-CoV-2 antibodies). This will identify participants who had SARS-CoV-2 exposure and immunity prior to commencement of the study.
  - The baseline blood samples will be analysed in batch months after randomisation, so there will be no clinically actionable results. We will provide individualised results to participants via email after completion of the trial.
     This email will be sent to the applicable HRECs to review before being sent out to any participant.
  - o In Brazil, IGRA testing will be completed on pre-randomisation and 12-month blood samples as outlined in appendix 4.
- At 3 months and 6 months (+ 42 days) post randomisation, the study team will
  coordinate to collect study blood samples from participants and in a subset of
  participants at 9 and 12 months (+ 42 days) post randomisation. This will identify

- participants who had an immune response to SARS-CoV-2 (surrogate marker of infection) during the study. This is needed to determine asymptomatic SARS-CoV-2 infections.
- Blood samples will also be taken for assessment of the immune system. This will be
  used to meet the planned exploratory analyses related to vaccine induced changes in
  the immune system. These blood samples will be taken at the same time as blood
  collection for serum or plasma samples (i.e. at randomisation and post
  randomisation)
- In the eventuality that it is unfeasible to collect swab samples to confirm SARS-CoV-2 infection at the time of febrile or respiratory illness episodes (or conduct a validated RAT test), seroconversion may be used to associate episodes of febrile or respiratory illness with SARS-CoV-2 infection. Therefore, for episodes of febrile or respiratory illness where a swab sample cannot be taken, 1 month after the onset of symptoms (expected peak post-infection antibody production), participants may be asked to come to the hospital to provide a blood sample. If rapid point-of care testing is available, these tests may be distributed to participants to self-test. Should these alternative methods of testing become required, an amendment will be submitted to HRECs to outline the process and submit any information for participants. This testing will not be conducted without further consultation with and approval from the HRECs, including providing the HRECs with details of the test and its efficacy.

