## 11.2 Population to be analysed

The primary analysis of all outcome data will be an intention-to-treat (ITT) analysis including all randomised participants, regardless of whether they received trial drug.

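### The primary analysis set and case definitions do not exclude infections already present at randomisation, so some primary events may be ones that BCG had little chance to prevent

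*Protocol*

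**What the plan says.** **Entry.** Section 4.3.3 excludes people who "Have previously had a SARS-CoV-2 positive test result", meaning PCR or an approved rapid antigen test. For acute illness it lists "Fever or generalised skin infection (where feasible, randomisation can be delayed until cleared". Cough, sore throat and shortness of breath are not listed, and no negative test is required.

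**Baseline sampling.** Everyone gives blood before randomisation, but section 7.3 states: "The baseline blood samples will be analysed in batch months after randomisation, so there will be no clinically actionable results". Only Brazil takes a swab. Appendix 4 says "Therefore after enrolment a baseline respiratory swab will be collected by the study nurse", and the schedule in 7.2 puts it in the inclusion and randomisation column. Appendix 4 adds: "Participants who return a positive SARS-CoV-2 result on the baseline swab will remain in the trial".

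**Outcomes.** Both primary definitions (synopsis and 3.2) need "a positive SARS-CoV-2 test (PCR, RAT or serology) over the 6 months following randomisation", plus fever or a respiratory symptom for outcome 1, or death, hospitalisation or non-hospitalised severe disease for outcome 2.

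**Analysis.** Section 11.2: "The primary analysis of all outcome data will be an intention-to-treat (ITT) analysis including all randomised participants, regardless of whether they received trial drug".

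**Where baseline status is used.** In 3.2, absence of exposure before randomisation is a condition for one secondary outcome, asymptomatic infection. In 11.3, baseline seropositivity defines a subgroup. Neither touches the primary analysis.

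**The concern.** The trial means to enrol people who have not had SARS-CoV-2, and section 7.3 says the baseline blood will identify those exposed earlier. Yet the two outcomes that decide the trial do not use that information. Three routes into the primary event count stay open:

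- A worker is incubating or has a cough on day 0, and a swab taken a day or two later is positive.
- A Brazilian participant is positive on the baseline swab, develops symptoms within days and is tested again.
- A participant has antibodies before randomisation, is still seropositive at 3 or 6 months, and reports a cough or sore throat in between. On the literal wording the serology branch accepts this.

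Randomisation spreads such people evenly between the arms. To the extent that BCG does not alter their course, they add the same number of events to each arm, dilute both risk ratios and cost power for severe COVID-19.

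**Working it through.** **1. The plan's own figure.** Inputs from 11.1: control risk 4%, risk ratio 0.667, two-sided alpha 0.04, power 80%, 1:1 allocation. The pooled-variance formula for two proportions, without continuity correction, with 0.04 against 0.04 × 2/3, gives 3038 per group, 6076 in total, exactly as stated. Allowing for 16% loss, 6076 / 0.84 = 7234, against the planned 7244. No term in this calculation allows for infections present at randomisation.

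**2. Dilution of the severe outcome.** Let p be the share already infected at randomisation, equal in both arms, and s the share of those who meet the severe definition. Neither is given in the protocol. Assume that BCG has no effect on these infections and that the planned risks hold for everyone else:

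- control risk = p·s + (1 − p) × 0.04
- BCG risk = p·s + (1 − p) × 0.02668, where 0.02668 = 0.04 × 0.667
- risk ratio = BCG risk / control risk
- share of control events already present = p·s / control risk

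Example, p = 2% and s = 20%: control 0.004 + 0.0392 = 0.0432; BCG 0.004 + 0.02615 = 0.03015; ratio 0.698; share 0.004 / 0.0432 = 9.3%.

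Power is for the same test with 3038 per group. The last column removes the infected, leaving 3038 × (1 − p) per group at 4% against 2.668%.

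| p | s | Risk ratio | Control events already present | Power, all randomised | Power, infected removed |
|---|---|---|---|---|---|
| 0 | – | 0.667 | 0% | 79.9% | 79.9% |
| 1% | 10% | 0.675 | 2.5% | 78.3% | 79.5% |
| 1% | 20% | 0.683 | 4.8% | 77.1% | 79.5% |
| 2% | 10% | 0.683 | 4.9% | 76.7% | 79.1% |
| 2% | 20% | 0.698 | 9.3% | 74.3% | 79.1% |
| 5% | 10% | 0.706 | 11.6% | 71.6% | 77.8% |
| 5% | 20% | 0.736 | 20.8% | 66.1% | 77.8% |

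**3. If the planned 4% already contains such cases.** Let f be their share of control events, so that the ratio is f + (1 − f) × 0.667. For f = 5%, 10% and 20% the ratio is 0.684, 0.700 and 0.734, and power is 75%, 70% and 59%. Removing those cases lowers the control risk to 3.6% at f = 10% and 3.2% at f = 20%, but power is then 75% and 70%.

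**4. Sensitivity to s.** The planning rates imply 4 / 55 = 7.3% of symptomatic cases severe. With s = 7.3% the ratio is 0.673, 0.679 and 0.696 at p = 1%, 2% and 5%.

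**5. Sensitivity to the no-effect assumption.** If BCG acted on existing infections with ratio k, the BCG risk would be k·p·s + (1 − p) × 0.02668. With k = 0.667 there is no dilution at all. At p = 5% and s = 20%, an illustrative k = 0.85 gives (0.0085 + 0.02535) / 0.048 = 0.705 instead of 0.736.

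**6. Symptomatic COVID-19.** The stated 2016 reproduces exactly with the continuity correction. At 1008 per group, power falls from 95% to 93%, 89% and 78% for f = 5%, 10% and 20%. The trial is sized on outcome 2, however, and at about 3038 evaluable per group power stays above 99.9%. The estimate is diluted; the test is not endangered.

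**The case against.** **Counting is inferred, not stated.** A reader might take the protocol to say that every baseline-positive is a BCG failure or a placebo case. It does not. Staying in the trial describes follow-up. A case also needs symptoms or severe disease, and the baseline swab itself is arguably not a test within the six months after randomisation. What stands is that nothing in the definitions stops a later positive test in the same infection from counting.

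**Not everyone infected gets through.** Known PCR or antigen positives and febrile people are excluded, and section 4.6 foresees that some consenters become sick and are not randomised. The gap concerns undetected, incubating or afebrile infection, and past infection known only from serology.

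**It may be settled in the statistical analysis plan.** Onset dates are collected, and event-dating rules are commonly left to that document. But the protocol itself fixes the primary set as all randomised and itself writes the case definitions, so the analysis plan would have to depart from stated text.

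**All-randomised is a legitimate estimand.** In an outbreak BCG might be given without testing. That is a fair question and a reason to keep the analysis, but it sits awkwardly with an eligibility rule meant to remove prior infection.

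**An existing infection need not be beyond BCG's reach.** Section 3.1 hypothesises that BCG shifts the whole severity curve. This objection stands: zero effect is an assumption, and step 5 shows that the dilution shrinks or vanishes without it.

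**The inputs are not the trial's.** This also stands. High transmission is mentioned only for Rio de Janeiro, and p is applied to the whole trial above. At 1–2% the shift is small.

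**Conclusion.** The point holds as a gap between the eligibility rule, the analysis set and the case definitions. Followed as written, infections present at randomisation that are or become symptomatic or severe, and baseline-seropositives who later report symptoms, can be primary events.

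The consequence is dilution towards no effect. A reader might infer a false-positive risk or an invalid comparison; neither follows, because the extra events fall equally on both arms.

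The size rests on three assumptions: the share infected, the share of those severe, and little or no BCG effect on them. For the severe outcome the risk ratio moves from 0.667 to about 0.675–0.698 with 1–2% infected, and to about 0.71–0.74 with 5%; power falls from 80% to 74–78% and to 66–72% respectively. The protocol does not support choosing one of these values. For symptomatic COVID-19 the matter is one of estimation, not power. The change is worth making because it is cheap, not because large harm has been shown.

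**What to change.** - **Section 11.2:** define the primary analysis set for both primary outcomes as randomised participants without evidence of SARS-CoV-2 on samples taken on or before the day of randomisation: baseline serology at all sites, the baseline swab in Brazil, and any other test sampled by that day.
- **Section 3.2 and synopsis:** state that an episode counts only if both symptom onset and the positive sample are after randomisation.
- **Section 11.3:** keep the all-randomised analysis as a sensitivity analysis and the baseline-seropositive subgroup as planned.
- **Appendix 4:** state that swab-positives are followed up but lie outside the primary set.

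Eligibility, treatment and visits do not change. The samples and onset dates are already collected. The set rests on samples from on or before the day of randomisation, so the arms stay comparable.

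The costs are a changed primary estimand, which needs an amendment before unblinding; a somewhat smaller analysed number (the last column of the table shows the net effect on power when every infected participant is identified); and uneven detection. Outside Brazil there is no baseline swab, so an early infection that has not yet produced antibodies would be removed only if another test had been sampled by day 0 or its symptoms had already begun. The onset rule also relies on self-report.

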#### **IGRA**

At randomisation, blood for anti-SARS-CoV-2 antibodies and IGRA will be taken for later assessment of seroconversion and TB infection. Therefore the initial blood sample in Brazil will be 35ml. This will identify participants who had TB exposure prior to commencement of the study. IGRA results will not exclude participants at consent & randomisation stage. Results will be shared with participants approximately 3 months after randomisation. A study doctor will follow-up with participants with positive IGRA to offer further assessment and treatment through government service provision.

At 12 months, blood for IGRA will be taken for later assessment to answer exploratory outcomes. Therefore the 12-month blood sample in Brazil will be 35 ml. This will identify participants who acquired TB during the study. Results will be shared with participants approximately 3 months after 12-month blood collection. A study doctor will follow-up with participants with positive IGRA to offer further assessment and treatment through government service provision.

